13.2.2. Severity Assessment

Severity Assessment – A qualitative assessment of the degree of intensity of an adverse event as determined by the Investigator or reported to him/her by the subject. The assessment of severity is made irrespective of test article, study treatment or study procedure relationship or seriousness of the event and should be evaluated according to the following scale:

- Mild – Event is noticeable to the subject, but is easily tolerated and does not interfere with the subject's daily activities
- Moderate – Event is bothersome, possibly requiring additional therapy, and may interfere with the subject's daily activities
- Severe – Event is intolerable, necessitates additional therapy or alteration of therapy and interferes with the subject's daily activities

13.3. Documentation and Follow-Up of Adverse Events

The recording and documenting of adverse events (ocular and non-ocular) begins when the subjects are exposed to the test article, study treatment or study procedure. Adverse events reported before the use of test article, start of study treatment, or study procedures will be recorded as medical history. However, if the condition deteriorates at any time during the study it will be recorded and reported as an AE. Untoward medical events reported after the subject's exit from the study will be recorded as adverse events at the discretion of the Investigator.

Upon finding an adverse event, the Principal Investigator will document the condition in the subject record and in the eCRFs. He/she will complete the Adverse Event /eCRF.

Complete descriptions of all adverse events must be available in the subject record. All Adverse Events including local and systemic reactions not meeting the criteria for "serious adverse events" shall be captured on the appropriate case report form or electronic data system. All adverse events occurring while the subject is enrolled in the study must be documented appropriately regardless of relationship.

It is the Investigator's responsibility to maintain documentation of each reported adverse event. All adverse events will be followed in accordance with applicable licensing requirements. Such documentation will include the following:

- Adverse event (diagnosis not symptom)
- Drawings or photographs (where appropriate) that detail the finding (e.g., size, location, and depth, etc.)
- Date the clinical site was notified
- Date and time of onset
- Date and time of resolution
- Adverse event classification, severity, and relationship to test articles, as applicable
- Treatment regimen instituted, including concomitant medications prescribed, in accordance with applicable licensing requirements
- Any referral to another health care provider if needed
- Outcome, ocular damage (if any)
- Likely etiology
- Best corrected visual acuity at the discovery of the event and upon conclusion of the event

In addition, if an infiltrate(s) is present, he/she will complete the Corneal Infiltrate Assessment eCRF. Where necessary, a culture of the corneal lesion will be collected to determine if the infection is microbial in nature. If cultures are collected, the date of culture collection and laboratory utilized will be recorded.

Changes in the severity of an AE shall be documented to allow an assessment of the duration of the event at each level of intensity to be performed. Adverse events characterized as intermittent require documentation of the onset and duration of each episode. Changes in the assessment of relationship to the Test Article shall also be clearly documented.

Subjects who present with an adverse event shall be followed by the Investigator, within licensure, until all signs and symptoms have returned to pre-treatment status, stabilized, or been satisfactorily resolved. If further treatment beyond licensure is required, the patient will be referred to the appropriate health care provider. The Investigator will use his/her clinical judgment as to whether a subject reporting with an adverse event will continue in the study. If a subject is discontinued from the study, it will be the responsibility of the Investigator to record the reason for discontinuation. The Investigator will also document the adverse event appropriately and complete the Adverse Event eCRF. Any subjects with ongoing adverse events related to the test article, study treatment or study procedures, as of the final study visit date, should be followed to resolution of the adverse event or until referral to an appropriate health care provider, as recommended by the Investigator. Non-ocular adverse events that are not related to the test article, study treatment, or study procedures may be recorded as “ongoing” without further follow-up.

13.4. Reporting Adverse Events

The Investigator will notify the Sponsor of an adverse event by e-mail, facsimile, or telephone as soon as possible and no later than 24 hours from discovery for any serious /significant adverse events, and 2 days from discovery for any non-significant adverse event. In addition, a written report will be submitted by the Principal Investigator to the IEC/IRB according to their requirements (Section 13.4.2). The report will comment whether the adverse event was considered to be related to the test article, study treatment or study procedures.

13.4.1. Reporting Adverse Events to Sponsor

Serious/Significant Adverse Events

The Investigator will inform the sponsor of all serious/significant adverse events occurring during the study period as soon as possible by e-mail, fax, or telephone, but no later than 24 hours following discovery of the event. The Investigator is obligated to pursue and obtain information requested by the Sponsor in addition to that information reported on the eCRF. All subjects experiencing a serious/significant adverse event must be followed up and all outcomes must be reported.

When medically necessary, the Investigator may break the randomization code to determine the identity of the treatment that the subject received. The Sponsor and study monitor should be notified prior to unmasking the test articles.

In the event of a serious/significant adverse event, the Investigator must:

- Notify the Sponsor immediately
- Obtain and maintain in the subject’s records all pertinent medical information and medical judgment for colleagues who assisted in the treatment and follow-up of the subject
- Provide the Sponsor with a complete case history which includes a statement as to whether the event was or was not related to the use of the test article
- Notify the IEC/IRB as required by the IEC/IRB reporting procedure according to national regulations

Unanticipated (Serious) Adverse Device Effect (UADE)

In the event of an Unanticipated (Serious) Adverse Device Effect (UADE), the Investigator will submit a report of the UADE to the Sponsor and IEC/IRB as soon as possible, but no later than 24 hours after the Investigator first learns of the effect. This report is in addition to the immediate notification mentioned above.

The Sponsor must conduct an evaluation of the UADE and must report the results of the evaluation to FDA, the IEC/IRB and participating Investigators within 10 working days after the Sponsor first receives notification of the effect.

Non-Serious Adverse Events

All non-serious adverse events, including non-serious adverse device effects, will be reported to the sponsor by the Investigator no later than 2 days from discovery.

13.4.2. Reporting Adverse Events to the Responsible IEC/IRB and Health Authorities

Adverse events that meet the IEC/IRB requirements for reporting must be reported within the IEC/IRB's written guidelines. Each clinical site will refer to and follow any guidelines set forth by their Approving IEC/IRB. Each clinical site will refer to and follow any guidelines set forth by their local governing Health Authorities.

The Sponsor will report applicable Adverse Events to the local health authorities according the written guidelines, including reporting timelines.

13.4.3. Event of Special Interest

None.

13.5. Reporting of Pregnancy

Subjects reporting pregnancy (by self-report) during the study will be discontinued after the event is recorded as an Adverse Event. Once discontinued, pregnant participants and their fetuses will not be monitored for study related purposes. At the Investigator's discretion, the study participant may be followed by the Investigator through delivery. However, this data will not be collected as part of the clinical study database. Pregnant participants are not discontinued from contact lens or solution related studies for safety concerns, but due to general concerns relating to pregnancy and contact lens use. Specifically, pregnant women are discontinued due to fluctuations in refractive error and/or visual acuity that occur secondary to systemic hormonal changes, and not due to unforeseen health risks to the mother or fetus.

14. STATISTICAL METHODS

14.1. General Considerations

All data summaries and statistical analyses will be performed using the SAS software Version 9.4 or higher (SAS Institute, Cary, NC). Throughout the analysis of data, the results for each subject/eye will be used when available for summarization and statistical analysis. Unscheduled visits will be summarized separately and will be excluded from the statistical analysis.

Summary tables (Descriptive statistics and/or frequency tables) will be provided for all baseline variables, efficacy variables and safety variables as appropriate. Continuous variables will be summarized with descriptive statistics (n, mean, standard deviation (SD), median, minimum and maximum). Frequency count and percentage of subjects or eyes within each category will be provided for categorical data.

Summaries will be presented by study lens type and will be performed separately by completion status. All analyses will be conducted on per-protocol population (see Section 14.3).

14.2. Sample Size Justification

A total of approximately 40 eligible subjects will be enrolled into the study at this site. At least 36 subjects will complete this study.

Using the POWER procedure in SAS 9.4, below is the summary of sample size required based on the different assumptions of the true LogMAR visual acuity and CLUE scores. The sample size was calculated for the non-inferiority tests (using 0.05 as the margin) with at least 90% of statistical power and 2-sided type I error of 0.05. Assuming the true LogMAR visual acuity is between 0.00 to 0.05 (distance) or 0.08 to 0.12 (near), and true CLUE vision score is between 38 to 42 points.

- Binocular LogMAR visual acuity (distance)

True Value	Estimated Standard Deviation	# of subjects needed	Actual Power
0.00	0.12	18	0.915
0.02	0.12	26	0.904
0.05	0.12	63	0.902

- Binocular LogMAR visual acuity (near)

True Value	Estimated Standard Deviation	# of subjects needed	Actual Power
0.08	0.12	21	0.905
0.10	0.12	33	0.901
0.12	0.12	63	0.902

- CLUE vision score

True Value	Estimated Standard Deviation	# of subjects needed	Actual Power
38	17	87	0.902
40	17	50	0.903
42	17	33	0.906

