2.3. Hypotheses

The following hypotheses will be tested throughout this investigation.

Primary Hypotheses

1. After 12-16 days of wear, the binocular bright, high contrast distance (4M) logMAR visual acuity of the test lens will be statistically better than +0.1 logMAR. This will be determined using ETDRS LogMAR acuity testing charts.
2. After 12-16 days of wear, the binocular bright, high contrast near (40cm) logMAR visual acuity of the test lens will be statistically better than +0.17 logMAR. This will be determined using Guillon/Poling LogMAR acuity testing charts.
3. After 12-16 days of wear, the PRO CLUE vision score for the test lenses will be statistically better than 32 points. This will be recorded by the subject using the CLUE follow-up questionnaire.

Secondary Hypotheses
Not applicable.

Other Hypotheses
Not applicable.

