14.5. Primary Analysis

LogMAR Visual Acuity

Binocular, high luminance, high contrast visual performance on logMAR scale will be analyzed using a linear mixed model. Each regression model will include the experimental design factors: distance as fixed effects. Other baseline characteristics known of importance such as age, gender, and/or add power will be included as fixed covariates when appropriate. Subject nested in site will be included as random covariates when appropriate. The covariance between residual errors from the same subject across different charts will be selected based on the finite-sample corrected Akaike's Information Criterion.⁶ Covariance structures considered may include: Homogenous compound symmetry (CS) and Unstructured covariance structure (UN). The structure that returns the lowest Akaike Information Criteria Corrected (AICC) will be selected as the structure that best fit the data.

Comparisons will be carried out using 95% confidence intervals constructed of least-square means (LSM) from the linear mixed models. Statistically superiority will be concluded if the upper limits of the confidence intervals are below the thresholds for corresponding distances.

CLUE Vision Scores

CLUE vision scores will be analyzed using a linear mixed model adjusting for baseline values as fixed covariate. The model will include the experimental design factors: time (6-8 day or 12-16 day) as fixed effects. Other baseline characteristics known of importance such as age, gender, and/or add power will be included as fixed covariates when appropriate. The covariance between residual errors from the same subject across different time will be selected based on the finite-sample corrected Akaike's Information Criterion.⁶ Covariance structures considered may include: Homogenous compound symmetry (CS) and Unstructured covariance structure (UN). The structure that returns the lowest Akaike Information Criteria Corrected (AICC) will be selected as the structure that best fit the data.

Comparisons will be carried out using 95% confidence intervals constructed of least-square means (LSM) from the linear mixed models for each time. Statistically superiority will be concluded if the lower limit of the confidence interval is greater than 32 points.

In all models, the Kenward and Roger method⁷ will be used for the calculation of the denominator of degrees of freedom.

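### The 90% power claim in Section 14.2 does not hold at 36 completers for four of the nine scenarios tabulated, and the tests are wrongly called non-inferiority

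*Combined protocol and SAP*

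**What the plan says.** Section 14.2 (Sample Size Justification) plans about 40 enrolled subjects and states: "At least 36 subjects will complete this study". It introduces its tables with "below is the summary of sample size required based on the different assumptions of the true LogMAR visual acuity and CLUE scores", and describes the calculation as follows: "The sample size was calculated for the non-inferiority tests (using 0.05 as the margin) with at least 90% of statistical power", with a two-sided type I error of 0.05. The assumed ranges are 0.00 to 0.05 logMAR for distance and 0.08 to 0.12 logMAR for near, and it assumes that the "true CLUE vision score is between 38 to 42 points". The SD is 0.12 for acuity and 17 for CLUE.

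Section 2.3 sets three primary hypotheses, each against a fixed threshold: distance acuity better than +0.1 logMAR, near acuity better than +0.17 logMAR, and "the PRO CLUE vision score for the test lenses will be statistically better than 32 points".

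Section 14.5 gives matching decision rules based on 95% confidence intervals. For acuity: "Statistically superiority will be concluded if the upper limits of the confidence intervals are below the thresholds for corresponding distances". For CLUE: "Statistically superiority will be concluded if the lower limit of the confidence interval is greater than 32 points". Neither section contains a 0.05 margin.

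**The concern.** There are two faults in the same sentence of Section 14.2.

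First, the section sets a 90% power statement, a range of assumed truths and a planned 36 completers side by side without connecting them. The tables themselves ask for more than 36 subjects in four of nine rows. A reader who takes the 90% at face value would treat a missed threshold as fairly strong evidence that the lens falls short of the assumed performance. In the less favourable part of each range that reading is not justified, because a miss there could easily be chance.

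Second, the sentence describes non-inferiority tests with a 0.05 margin, whereas the hypotheses and decision rules are superiority tests against fixed values. From Section 14.2 alone a reader cannot tell what was powered. For CLUE, with an SD of 17 points, a margin of 0.05 makes no sense.

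**Working it through.** **Inputs.** Two-sided alpha 0.05, SDs of 0.12 and 17, the true values, and the planned 36 completers and 40 enrolled come from Section 14.2. The thresholds 0.10, 0.17 and 32 come from Section 2.3.

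**Method.** One-sample t-test. With difference d = |true value − threshold|, the noncentrality is √n × d/SD on n − 1 degrees of freedom, and power is the probability that the noncentral t statistic falls beyond the two-sided 5% critical value.

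**Step 1: reproduce the plan.** The smallest n giving at least 90% power, with no margin, is 18, 26, 63 (distance), 21, 33, 63 (near) and 87, 50, 33 (CLUE). All nine match the plan, as do all nine printed power values. The tables were therefore computed as superiority tests against the Section 2.3 thresholds, or by something numerically identical.

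**Step 2: the same function at the planned size.** At n = 36, √n = 6, so distance 0.05 has noncentrality 6 × 0.05/0.12 = 2.50 and CLUE 38 has 6 × 6/17 = 2.12.

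| Endpoint, true value | d | n in plan | Power at 36 | Power at 40 |
|---|---|---|---|---|
| Distance 0.00 | 0.10 | 18 | 0.998 | 0.999 |
| Distance 0.02 | 0.08 | 26 | 0.973 | 0.984 |
| Distance 0.05 | 0.05 | 63 | **0.681** | **0.729** |
| Near 0.08 | 0.09 | 21 | 0.992 | 0.996 |
| Near 0.10 | 0.07 | 33 | 0.925 | 0.949 |
| Near 0.12 | 0.05 | 63 | **0.681** | **0.729** |
| CLUE 38 | 6 | 87 | **0.540** | **0.586** |
| CLUE 40 | 8 | 50 | **0.784** | **0.827** |
| CLUE 42 | 10 | 33 | 0.929 | 0.952 |

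Five of nine rows reach 90% at 36. CLUE does so only at its most favourable value.

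**Step 3: where 36 does give 90%.** The standardised difference needed is 0.5557. This translates to:
- distance: 0.10 − 0.5557 × 0.12 = 0.033 or better
- near: 0.17 − 0.5557 × 0.12 = 0.103 or better
- CLUE: 32 + 0.5557 × 17 = 41.4 (41.45 before rounding), so about 41.5 or more

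Alternatively, the SD would have to be smaller than assumed: 0.05/0.5557 = 0.090 instead of 0.12 for the two short acuity rows, and 6/0.5557 = 10.8 (CLUE 38) or 8/0.5557 = 14.4 (CLUE 40) instead of 17.

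**Step 4: credit for baseline adjustment.** Section 14.5 adjusts CLUE for its baseline value, but the documents give no correlation. Taking a correlation r as an assumption, the residual SD is 17√(1 − r²) and there are 34 degrees of freedom. At r = 0.3, power at 36 is 0.578 (CLUE 38) and 0.820 (CLUE 40); at r = 0.6 it is 0.730 and 0.929. Reaching 90% needs r of about 0.53 for CLUE 40 and 0.77 for CLUE 38.

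**Step 5: can the margin wording be rescued?** For acuity, benchmarks of 0.05 and 0.12 plus a 0.05 margin give 0.10 and 0.17, and hence the same six n. The documents state no such benchmarks. Adding 0.05 beyond the stated acuity thresholds would give 9, 12, 18 and 10, 13, 18, which do not match. For CLUE, shifting the threshold by 0.05 points gives 85, 49, 33, not the printed 87, 50, 33.

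**The case against.** The best defence is that the tables are a grid of scenarios. On that reading the 90% is the target used to solve for n in each row, every row meets it, and no sentence says outright that 36 completers give 90% across the ranges. The larger n are printed in plain view. This is fair as far as it goes: nothing is hidden and no table entry is wrong. But a sample size justification must say which scenario the chosen number rests on, and this one does not. The power at 36 appears nowhere.

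A second defence draws on the earlier hyperopic cohorts in Section 1.5. Their mean distance acuities were −0.049 (57 subjects), 0.066 (19) and −0.023 (62), and their near means 0.059, 0.103 and 0.103. Weighted by size:
- distance: (57 × −0.049 + 19 × 0.066 + 62 × −0.023)/138 = −0.021
- near: (57 × 0.059 + 81 × 0.103)/138 = 0.085

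At both values 36 gives more than 90%. So the weak acuity rows are mostly the pessimistic ones, which deserves weight. Two of the three near means nevertheless sit right at the 90% boundary (0.103 gives 0.903), and one distance mean is worse than the whole assumed range. The documents give no earlier CLUE mean, so this defence does not reach CLUE, where the shortfall is largest.

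Third, the planned mixed models may gain precision from covariates. Step 4 quantifies this for CLUE. For acuity, age, gender and add power may be included, and any gain is unquantified.

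Finally, the non-inferiority wording changes no n, threshold or decision rule. That is true, and it makes the correction editorial, but the text still contradicts Sections 2.3 and 14.5.

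**Conclusion.** The concern holds and should be fixed. With 36 completers, four of nine scenarios fall below the stated 90%: distance 0.05 and near 0.12 at 68%, CLUE 38 at 54% and CLUE 40 at 78%. With all 40 analysed they reach 73%, 73%, 59% and 83%. A lens with a true CLUE mean of 38, six points above the threshold, would miss in roughly 46% of such studies.

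These figures rest on the plan's own SDs, thresholds and unadjusted one-sample t-test, and apply to each endpoint separately. Baseline adjustment could close the gap for CLUE 40 at a moderately strong correlation; for CLUE 38 it would take about 0.77. The harm is an overstated planning claim: the risk of a false success is unaffected. The non-inferiority label is wrong for all three tests as Sections 2.3 and 14.5 define them.

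**What to change.** Keep 36 completers and revise Section 14.2:

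- Replace the general 90% statement with the power at 36 for each of the nine rows.
- State that, before any covariate adjustment, 36 gives 90% power only if true distance acuity is about 0.033 or better, near acuity about 0.103 or better, and CLUE about 41.5 or more.
- If the sponsor relies on baseline adjustment for CLUE, state the correlation assumed.
- Describe the tests as one-sample superiority tests against 0.10, 0.17 and 32, and remove the reference to a 0.05 margin.

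The cost is wording in one section and a less favourable stated power. Endpoints, thresholds, analysis and conduct do not change, and no subjects are added. Covering every row at 90% by the plan's method would instead need 87 completers.

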14.3. Analysis Populations

Safety Population:

All subjects who were administered any test article excluding subjects who drop out prior to administering any test article. At least one observation should be recorded.

Per-Protocol Population:

All subjects who have successfully completed all visits and did not substantially deviate from the protocol as determined by the trial cohort review committee prior to database hard lock (Per-Protocol Population). Justification of excluding subjects with protocol deviations in the per-protocol population set will be documented in a memo to file.

Intent-to-Treat (ITT) Population:

All assigned subjects regardless of actual treatment and subsequent withdrawal from study or deviation from protocol. At least one observation should be recorded.

14.4. Level of Statistical Significance

All planned analysis for this study will be conducted with an overall type I error rate of 5%.

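### The plan promises an overall 5% type I error for three primary hypotheses but gives no success rule: separate claims can reach about 7.5%, and requiring all three gives joint power of 25% to 92% at 36 completers

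*Combined protocol and SAP*

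**What the plan says.** - **Error rate.** Section 14.4 (Level of Statistical Significance): "All planned analysis for this study will be conducted with an overall type I error rate of 5"%. It gives neither sidedness nor a multiplicity method.
- **Hypotheses.** Section 2.3 opens with "The following hypotheses will be tested throughout this investigation" and numbers three primary hypotheses, all after 12-16 days of wear: "high contrast distance (4M) logMAR visual acuity of the test lens will be statistically better than +0.1 logMAR"; "high contrast near (40cm) logMAR visual acuity of the test lens will be statistically better than +0.17 logMAR"; and a CLUE vision score better than 32 points.
- **Acuity decision.** Section 14.5 (Primary Analysis): "Statistically superiority will be concluded if the upper limits of the confidence intervals are below the thresholds for corresponding distances". The intervals are 95% intervals.
- **CLUE decision.** Section 14.5 compares the lower 95% limit with 32 points. The intervals come from "least-square means (LSM) from the linear mixed models for each time", meaning 6-8 days and 12-16 days, although Hypothesis 3 names only 12-16 days.
- **Sample size.** Section 14.2 sizes each endpoint on its own, "with at least 90% of statistical power and 2-sided type I error of 0.05". It targets 36 completers from about 40 enrolled and gives no joint power.

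No section says whether study success needs one, two or all three hypotheses. No testing order or adjustment is given.

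**The concern.** An overall error rate belongs to a decision rule, and the plan does not state that rule. Two are open, and each has a consequence that the plan does not report.

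If each hypothesis may be claimed on its own interval, there are three chances of a false claim and nothing holds the total at 5%. If all three must be met, the error is safe, but the study's power is then the probability of passing all three tests. The table in 14.2 does not show that.

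The practical stake is a mixed result. If two hypotheses are met and one is missed, the plan offers no predefined reading, so whether the study succeeded could be settled after the data are seen. At the plan's most favourable and middle values, CLUE is the endpoint most likely to miss.

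**Working it through.** **1. Reproducing the sample size table (14.2).** Inputs: thresholds 0.10, 0.17 and 32 (2.3); SD 0.12 for acuity and 17 for CLUE, with the tabled true values (14.2); two-sided alpha 0.05 (14.2). Method: exact one-sample t-test with noncentrality √n × |threshold − true value| / SD and n − 1 degrees of freedom. All nine rows reproduce:

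| Endpoint | True value | n | Power |
|---|---|---|---|
| Distance | 0.00 / 0.02 / 0.05 | 18 / 26 / 63 | 0.915 / 0.904 / 0.902 |
| Near | 0.08 / 0.10 / 0.12 | 21 / 33 / 63 | 0.905 / 0.901 / 0.902 |
| CLUE | 38 / 40 / 42 | 87 / 50 / 33 | 0.902 / 0.903 / 0.906 |

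Section 14.2 calls these "non-inferiority tests (using 0.05 as the margin"), but the rows reproduce only as superiority tests against the thresholds, with no added margin. That agrees with 2.3 and 14.5, so the calculation below uses superiority.

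**2. Error if the three are claimed separately.** Only one end of each 95% interval counts as success, so each test carries 2.5%. With all three true values at their thresholds:
- Independent: 1 − 0.975³ = 0.073.
- Upper bound under any dependence: 3 × 0.025 = 0.075.
- Equal correlation (assumed; the documents give none), Gaussian model: 6.3% at 0.5, 5.5% at 0.7, 4.9% at 0.8.

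With only two true values at threshold the figure is 1 − 0.975² = 0.049, bound 5.0%. The excess therefore arises when the lens is no better than threshold on all three.

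**3. Error if all three are required.** A false overall success needs at least one false rejection of a particular true null, which has probability at most 2.5%. Section 14.4 is then met without adjustment.

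**4. Marginal power at 36 completers.** Here √36 = 6, so, for example, the noncentrality is 6 × 0.08 / 0.12 = 4.0 for distance at 0.02 and 6 × 8 / 17 = 2.82 for CLUE at 40.

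| | Most favourable (0.00, 0.08, 42) | Middle (0.02, 0.10, 40) | Worst (0.05, 0.12, 38) |
|---|---|---|---|
| Distance | 99.8% | 97.3% | 68.1% |
| Near | 99.2% | 92.5% | 68.1% |
| CLUE | 92.9% | 78.4% | 54.0% |

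**5. Joint power at 36 completers.**
- Most favourable, independent: 0.998 × 0.992 × 0.929 = 0.92. At correlation 0.5: 92.4%.
- Middle, independent: 0.973 × 0.925 × 0.784 = 0.71. At 0.5: 74.5%.
- Worst, independent: 0.681 × 0.681 × 0.540 = 0.25. At 0.5: 37.9%.

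Under any dependence, joint power cannot exceed the weakest margin. That is a ceiling of 78.4% if true CLUE is 40 and 54.0% if it is 38. Under independence, 26 of the 27 combinations of tabled values fall below 90%, one of them at 89.7%. CLUE alone needs a true mean of about 41.5 for 90% power.

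**The case against.** **The rule is unstated, which is not the same as breached.** The synopsis and Section 2.2 name two primary endpoints, acuity and subjective response, and the acuity rule in 14.5 is worded in the plural. It can be read as one decision needing both distances. Two decisions at 2.5% each give 1 − 0.975² = 4.9%, bound 5.0%, which would satisfy 14.4. This reading is possible but strained, because 2.3 numbers distance and near as separate hypotheses with separate thresholds. What stands is that the text does not settle the matter.

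**Independence is not neutral.** Both acuities come from the same subjects in one mixed model, and positive correlation lowers the error and raises the joint power. This stands, and it is why ranges are given. The excess over 5% goes away only at a correlation of about 0.8, and the CLUE ceilings need no correlation assumption.

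**The low power figures are mostly marginal.** Section 14.2 openly shows CLUE needing 50 or 87 subjects at 40 or 38, and each acuity endpoint needing 63 at its worst value. This also stands. Requiring all three costs less by itself: where every endpoint alone reaches 90% at 36 completers, the lowest joint figure is 0.973 × 0.925 × 0.929 = 0.84.

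**Stronger readings that a reader might infer.**
- *Joint power is below 90% throughout.* It is not: at the most favourable values it is about 92%, and 34 completers would be enough for 90%.
- *Three tests at 5% give about 14%.* Only one direction counts as success, so the per-test error is 2.5%.
- *The 6-8 day CLUE interval adds a fourth claim, giving 1 − 0.975⁴ = 9.6%.* No hypothesis covers 6-8 days, and producing an interval there is not a claim. Independence is also least plausible for two scores from the same person a week apart.

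**Conclusion.** The point holds as a missing success rule. Section 14.4 states an overall 5% that Sections 2.3 and 14.5 do not secure. Under separate claims the familywise error is up to about 7.5% (7.3% independent, 6.3% at correlation 0.5). This is a moderate excess, measured against 5% in the favourable direction, which is the lenient reading of 14.4. Under an all-three rule the error is at most 2.5%, and joint power at 36 completers is 92%, 71% or 25% across the most favourable, middle and worst planning values. It is capped at 78% or 54% if true CLUE is 40 or 38.

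These figures rest on the plan's own SDs and true values and on one-sample t-tests as in 14.2. The planned mixed models with covariates could have somewhat different power. The correlations are assumptions. Section 1.5 reports acuity from earlier studies of the lens system but no CLUE result, so nothing shown locates true CLUE within 38 to 42. The documents do not show that 5% is necessarily exceeded or that the study is underpowered at every planning value.

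**What to change.** - **14.4:** State that the primary objective is met only if all three hypotheses in 2.3 are met at 12-16 days, each judged on its 95% interval, with no alpha adjustment. If separate claims are wanted, name Holm across the three instead and say whether the 5% is one-sided or two-sided.
- **14.5:** Base the CLUE decision on the 12-16 day least-squares mean only, as Hypothesis 3 does, and label the 6-8 day interval descriptive.
- **14.2:** Report the marginal and joint power that 36 completers give over the planning values, with the correlation assumption.

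**Cost.** A few sentences and a less favourable stated power, with no extra subjects. Disclosure does not raise the power: under independence, 90% joint power would take 53 completers at the middle values and 98 at the worst. Holm has its own price. If its first step uses two-sided 0.05/3, CLUE power at that step with 36 completers is 83.9% at a true score of 42 and 62.3% at 40.
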